17. RECORDS

The Clinical Research Division at the FHCRC maintains a patient database that allows for the storage and retrieval of specific types of patient data including demographic

information, protocol registration information, and data from the treatment course. These data are collected from a wide variety of sources and conform to institutionally established guidelines for coding, collection, key entry, and verification. Each patient will be assigned a unique patient number (UPN) to assure patient confidentiality. Any publication or presentation will refer to patients by this number and not by name. Information about patients enrolled on this protocol that is forwarded to agencies such as the FHCRC IRB, EMD Serono, Inc., NIH, and FDA will refer to the patients only by their UPN.

Original inpatient and outpatient medical records will be maintained by the medical records departments at the institutions where the patients receive their care. The majority of their care related to this protocol will be received at the SCCA and UW Medical Center. The study nurse and/or data coordinator will maintain a Case Report Form (CRF) Notebook for each patient treated on this protocol. The CRF notebooks and their contents will be identified by the patient's initials and UPN only. All supporting documents used to verify the accuracy of the data in the case report forms will be kept separately. Patient research files will be kept in a locked, controlled-access building. At least monthly, the PI or a designated co-investigator will review and cross check the data entered on the case report forms with the source documents.

18. STATISTICAL CONSIDERATIONS

The **primary objective** of this trial is to assess and compare the safety and potential efficacy associated with treating patients who developed metastatic MCC by combined MHC up-regulation and anti-PD-L1 antibody treatment (Group 1); and combined MHC up-regulation, anti-PD-L1 antibody treatment, and adoptive transfer of MCPyV TAg-specific polyclonal autologous CD8⁺ T cells (Group 2). The treatment for each group will be considered to have an acceptable safety profile, if the observed toxicity rate is consistent with a true rate that does not exceed 30%, whereas toxicity is defined in **Section 13**. The potential efficacy of treatment within each group will be assessed primarily by examining the time from first to second metastasis. Among 49 patients who would be considered eligible for this trial and who received standard treatment (localized radiation or chemotherapy) at UW, the median time to second metastasis was an estimated 200 days (**Figure 146**). This is the benchmark that we shall use in the current trial for assessment of potential efficacy.

[figure not shown]

Figure 146. Observed and predicted times to second metastasis

A total of 20 patients will be treated in the trial, including 10 in each of Groups 1 and 2 as long as the level of safety is deemed to be acceptable. This number was not derived based on any formal statistical considerations; rather, it is a number that is a compromise between the number of patients that can be enrolled in a reasonable time frame and the number of patients whose treatment will provide enough information to gain a preliminary assessment of efficacy. From our database of over 850 patients, we are in active contact with ~300 living MCC patients. Approximately 120 new patients are recruited each year to our cohort. One-third of MCC patients will have a first metastasis within 3 years of diagnosis. Each year, approximately 40 patients in our cohort experience a first metastasis. Because we now have tetramers that cover >80% of MCC patients based on their HLA alleles, we anticipate that generation of functional tetramer-positive MCPyV-specific T cells from the peripheral blood will be feasible on a sufficient number of cases so that we can readily meet targeted enrollment of four cases per year.

The observed time to second metastasis for the 49 patients is summarized in **Figure 146**. Based on these data, and in collaboration with our study biostatistician ([name]), we fit a piecewise exponential model wherein we assumed a constant hazard of metastasis in each of nine different time windows as a means of specifying an assumed-true distribution for time to metastasis. At the end of each window, the assumed-true probability of metastasis is required to equal the observed value at this time. From this assumed-true distribution, the assumed-true distribution for the current

therapy was generated by assuming a hazard of failure that is proportional to that from the assumed-true distribution from the historical data. From this distribution, 5,000 simulated trials were randomly generated, and the lower limit of a point-wise confidence interval was estimated for each simulated trial. The proportion of trials where this confidence limit exceeded 200 days was taken as the estimated power to observe a statistically significantly improved median time to metastasis compared to the fixed time of 200 days. **Table 8** below summarizes the power estimated in this manner for a variety of assumed-true distributions and one-sided significance (α) levels with 10 patients.

Therefore, with 10 patients treated, we'll have sufficient power to observe a statistically significant improvement in median time to metastasis relative to the fixed historical time of 200 days for scenarios with assumed-true parameters as summarized above. For the analysis, we will use 'Time 0' as the first day of treatment as opposed to the time of 1st metastasis. Potential efficacy of Groups 1 and 2 will be assessed in this manner. If each group is deemed to be potentially efficacious, then we will use a "play-the-winner" approach to choose the treatment that will move forward to our next trial, wherein the group with the longest median time to metastasis will be declared the winner. If only one group is deemed to be potentially efficacious as described above, then this is the treatment that will be taken forward. If neither treatment is considered to be potentially efficacious, then neither treatment will be taken forward.

Table 8. Power estimates

Assumed-true Median	Assumed-true Hazard Ratio	Significance level of 0.10	Significance level of 0.15
352 days	3	70%	88%
411 days	4	85%	92%

Secondary efficacy endpoints include response to treatment by RECIST criteria and MCC-specific survival. Although we will report the overall response rate (See **Section 12.D.2**) using RECIST criteria to determine clinical responses in all patients, radiation therapy or intralesional IFN β -1B injection may have an independent effect on the targeted metastasis (see **Section 12.D.1**) and may not adequately capture the effect of transferred T cells or anti-PD-L1 antibody treatment. Furthermore, it is estimated that 10 patients will not be sufficient to evaluate the effect of this treatment on MCC-specific survival.

However, in patients who had both lesions which did and did not receive MHC Class I upregulation interventions, we will report the rate of response of either group of lesions. Response assessment will be carried out per RECIST v1.1 in all lesions which received MHC Class I upregulation and all lesions which did not receive MHC Class I upregulation. Responses will be classified as CR, PR, SD or PD per RECIST definitions. The Objective response rate (ORR) and 90% confidence interval will be calculated as the proportion of evaluable lesions that achieve a CR or PR. The ORR for lesions which

did and did not receive MHC Class I upregulation will be calculated separately, and confidence intervals will account for correlation of lesions within a patient.

The study will be suspended pending a review by the DSMB if there is ever sufficient evidence to suggest that the true toxicity rate exceeds 30% in any group. In terms of toxicity of conventional therapy, fractionated ionizing radiation of 30-60Gy is typically effective in controlling the target MCC lesion, but it is commonly associated with transient grade ≤ 3 local toxicities such as mucositis and erythema, depending on the target site. However, radiation therapy cannot be used to repetitively control multiple recurrences.⁸¹ The rate of grade ≥ 3 toxicities associated with platinum-based chemotherapy regimens for the systemic treatment of MCC is approximately 30% to 40%.⁸² Thus, in order not to exceed the toxicity rate induced by standard systemic treatment, enrollment to any group will be suspended if evidence suggests that the true toxicity rate exceeds 30%. Sufficient evidence will be taken to be an observed proportion of toxicities for which the associated lower 80% confidence limit exceeds 30%. Operationally, this limit will be met if any of the following proportions is observed: 2/2-3, 3/4-5, 4/6-8, 5/9-10. Based on this rule, if the true probability of toxicity is 10%, the probability of suspending one group after 10 patients is approximately 0.03. If the true probability of toxicity is 50%, the probability of suspension is 0.76.

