7. ELIGIBILITY FOR TREATMENT

7.A. Inclusion Criteria

1. Signed written informed consent.
2. Confirmation of MCC by internal pathology review of initial or subsequent biopsy or other pathologic material.
3. If an accessible lesion is present, a biopsy will be performed within 6 weeks of the start of study intervention. The results of the biopsy must be obtained prior to initiation of study intervention.
4. Evidence of MCPyV TAg tumor expression by immunohistochemistry on any prior or current tumor specimen or viral oncoprotein antibody confirmation within 6 weeks of the start of study intervention.
5. ECOG PS ≤ 2 at trial entry.
6. 18 years of age or older.
7. Patients must have at least one bi-dimensionally measurable lesion by palpation, clinical exam, or radiographic imaging within 6 weeks of the start of study intervention (X-ray, CT scan, PET scan, MRI, or Ultrasound).
8. For patients designated to be treated on Group 2: cardiac ejection fraction ≥35%. For patients with significant risk factors for coronary artery disease (Framingham risk score > 15%), a cardiac stress test is recommended.
9. At least 3 weeks must have passed since any of the following: systemic corticosteroids, immunotherapy (for example, T-cell infusions, immunomodulatory agents, interleukins, MCC vaccines, intravenous immunoglobulin, expanded polyclonal TIL or LAK therapy), pentoxifylline, other small molecule or chemotherapy cancer treatment, other investigational agents **or other systemic agents that target Merkel cell carcinoma.**

7.B. Exclusion Criteria

1. Known active infections or oral temperature >38.2 C fewer than 72 hours prior to receiving study treatment or systemic infection requiring chronic maintenance or suppressive therapy.
2. CBC profile prior to trial entry:

WBC < 2000/mcl
Hb < 8 g/dL
ANC < 1000/mcl
Platelets < 50,000/mcl

3. New York Heart Association functional class III-IV heart failure, symptomatic pericardial effusion, stable or unstable angina, symptoms of coronary artery disease, congestive heart failure, clinically significant hypotension, or history of an ejection fraction of $\leq 30\%$ (echocardiogram or MUGA).
4. Clinically significant pulmonary dysfunction, as determined by medical history and physical exam. Patients so identified will undergo pulmonary functions testing and those with FEV1 < 2.0 L or DLco (corr for Hgb) < 50% will be excluded.
5. Creatinine clearance < 30 ml/min which cannot be attributed to MCC metastasis.

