11. PLAN OF TREATMENT

Group 1

Group 2

[figure not shown]

Figure 14. Treatment schema

1. Initial Evaluation/Consent (all Groups)

Patients will be screened for their eligibility on the study and consented during this visit. Baseline anthropometry will be obtained.

2. Administration of Avelumab (Groups 1 and 2)

Subjects will receive an IV infusion of Avelumab within 4 weeks of the baseline staging scans at a dose of 10 mg/kg over the duration of 1 hour (-10/+20 minutes) following pretreatment with H1 blockers (diphenhydramine 12.5mg to 50 mg PO or IV, or equivalent), and acetaminophen po 500 to 650 mg, once every 2 weeks (See **Appendix B**). The dose of Avelumab will be calculated based on the weight of the subject determined at trial entry. Following Avelumab infusions, subjects will be observed for 1 hour post infusion for potential infusion-related reactions. Subjects will receive Avelumab once every 2 weeks for 12 months or until the criteria in **Section 13.G.** (Off Study Criteria) are met. Modifications of the infusion rate due to infusion-related reactions are described in **Section 13.C.**

In this trial, subjects will receive Avelumab IV infusions at the SCCA. Well trained medical staff will monitor and perform the trial drug administration.

3. MHC class I up-regulation: Radiation or intralesional IFN β -IB injection

Radiation therapy or intralesional IFN β -1B injection will be scheduled as an outpatient treatment at the SCCA or the University of Washington Medical Center (UWMC) between 7 and 10 days after the preceding dose of Avelumab (for Groups 1 and 2) and within 2 to 5 days prior to a subsequent T-cell infusion (Group 2).

4. T-Cell Infusions

T-cell infusions will be given at the Seattle Cancer Care Alliance at least 48 hours after MHC class I upregulation and preferably at least 48 hours before the next dose of Avelumab. All patients will be observed for 2 hours post infusion and will be released if no AE requiring prolonged hospitalization have occurred (see **Section 13**).

T cells will be infused intravenously at a rate of not more than 500 cc/hour through an 18- or 20-gauge catheter inserted into a peripheral vein or through a central catheter. The infusion bag will be gently mixed periodically during the infusion. Subjects will have vital signs per **Section 12.B**.

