All patients treated on this protocol will have developed metastatic disease. It is plausible that up-regulation of MHC class I with either radiation therapy or intralesional IFN β -1B injection may have an independent effect on the targeted metastasis (as assessed by RECIST criteria). It is unlikely however, that localized radiation or intralesional interferon will have a significant effect on the risk of distant disease development. In contrast, T-cell infusions and/or anti-PD-L1 have the potential to generate a broader systemic effect by preventing the occurrence of new distant metastasis. To assess the potential systemic effects of adoptively transferred T cells, the time for a new metastasis to develop after treatment will be assessed, and this parameter will be compared to historical matched controls undergoing standard therapy. A preliminary assessment was carried out on 49 of the MCC patients in our cohort who originally presented with local or regional disease and later developed metastatic disease, at which time they underwent standard therapy (radiation or chemotherapy). Patients with systemic immune suppression were eliminated from the analysis as they would not be candidates for the combined MHC and T-cell therapy trial. Among these patients, the median time to developing a new metastasis was 200 days (see **Section**

18 for further statistical details). Patients will be followed and restaged at least once every 3 months and as clinically indicated after 12 months since the last infusion has elapsed until new metastasis occur (see **Appendix B**).

12.D.2 Clinical response by RECIST criteria (secondary endpoint)

Tumor lesions and tumor responses will be assessed according to the **Response Evaluation Criteria in Solid Tumors (RECIST) v 1.1**. Radiographic imaging and clinical assessment of residual disease will be compared with pre-infusion assessment.

Responses will be reported separately for lesions which did or did not receive MHC Class I upregulation interventions, if the latter are present. Overall responses will be reported as well.

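### Section 18 words the 200-day benchmark as first-to-second-metastasis time but starts the trial clock at first treatment; the readable text does not show that the two match

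*Combined protocol and SAP*

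**What the plan says.** Section 18 states that potential efficacy in each group "will be assessed primarily by examining the time from first to second metastasis". It gives the benchmark in the same terms: a median time to second metastasis of 200 days in 49 patients on standard treatment. A piecewise-exponential curve is fitted to those 49 patients, and Table 8 reports the power to detect an "improvement in median time to metastasis relative to the fixed historical time of 200 days".

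The same section then sets Time 0 for the analysis "as the first day of treatment as opposed to the time of 1st metastasis". The 200 days is not re-estimated on that clock.

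Section 12.D.1 words the primary endpoint differently: "the time for a new metastasis to develop after treatment will be assessed, and this parameter will be compared to historical matched controls". Of the historical patients it says that they presented with local or regional disease and "later developed metastatic disease, at which time they underwent standard therapy". It does not say from which day their 200 days was counted.

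For trial patients, inclusion criterion 7 (Section 7.A) asks for "at least one bi-dimensionally measurable lesion by palpation, clinical exam, or radiographic imaging within 6 weeks of the start of study intervention". Section 11, item 2 adds: "Subjects will receive an IV infusion of Avelumab within 4 weeks of the baseline staging scans". Neither rule dates a first metastasis.

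**The concern.** The plan itself treats first metastasis and first treatment as different starting points, chooses the second for the trial, and leaves the benchmark as it was. Two readings of the historical clock are open.

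- **Counted from first metastasis.** The two clocks then differ by each trial patient's time from first metastasis to first study treatment. No readable passage limits that time. Criterion 9 allows earlier therapy after a 3-week interval, and Section 6 lets a Group 1 patient who progresses resume on Group 2.
- **Counted from start of standard therapy.** The clocks then match. What remains is a possible difference between the cohorts in time since first metastasis at entry.

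The comparison with 200 days decides whether each group is called potentially efficacious and can be taken forward. If 200 days is not the median expected with no effect on the trial clock, the rule is too strict or too lenient by an unstated amount.

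**Working it through.** **Inputs.** From Section 18 and Table 8: 10 patients per group; historical median 200 days; assumed-true medians of 352 days (hazard ratio 3) and 411 days (hazard ratio 4); power 70%/88% and 85%/92% at one-sided 0.10/0.15. The hazard ratio is read as historical over new, since a ratio above 1 goes with a longer median. The nine window hazards and Figure 146 are not readable.

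**Step 1: historical curve implied by Table 8.** Under proportional hazards S_new(t) = S0(t)^(1/HR), so a new median m means S0(m) = 0.5^HR.

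- S0(200) = 0.5; S0(352) = 0.5^3 = 0.125; S0(411) = 0.5^4 = 0.0625.
- Average daily hazard, days 0-200: ln 2/200 = 0.0035.
- Days 200-352: 2 ln 2/152 = 0.0091.
- Days 352-411: ln 2/59 = 0.0118.

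The average hazard is not constant, so moving the origin can change the median.

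**Step 2: reproduce Table 8.** Without censoring, whether the lower limit for the median exceeds 200 days depends on the number of events among 10 by day 200. The nearest rules are at most 2 events (0.10) and at most 3 events (0.15). The event probability is 1 - 0.5^(1/HR): 0.206 for ratio 3 and 0.159 for ratio 4.

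- Ratio 3: 66%/87%, against 70%/88% in Table 8.
- Ratio 4: 80%/94%, against 85%/92%.
- No effect (probability 0.5): false-pass rate 5.5%/17.2%.

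The 0.15 column is matched within 2 points. The 0.10 column is not matched exactly. Without the window hazards this is no ground for calling Table 8 wrong, but the figures below come from an approximated rule.

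**Step 3: illustrate a gap.** Assume that the 200 days runs from first metastasis and that every trial patient starts d = 28 days later with no second metastasis yet. The 28 days is an assumption, not a figure that the plan gives for this gap. The no-effect probability of being event-free 200 days after treatment start is S0(228)/S0(28). Its cumulative hazard is

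ln 2 - (hazard over days 0-28) + (hazard over days 200-228).

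Keep the hazard flat over days 0-200, so the first 28 days carry 28 × 0.003466 = 0.097. Then vary the hazard just after day 200:

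| Hazard, days 200-228 | Cumulative hazard | Power at ratio 3 (at most 2 / at most 3) | False pass |
|---|---|---|---|
| Table 8 average for days 200-352 | 0.693 - 0.097 + 0.255 = 0.851 | 53%/78% | 1.9%/7.7% |
| Same as before day 200 | 0.693 - 0.097 + 0.097 = 0.693 | 66%/87% | 5.5%/17.2% |
| Zero | 0.693 - 0.097 + 0 = 0.596 | 74%/91% | 10%/27% |
| Twice that average | 0.693 - 0.097 + 0.511 = 1.107 | 36%/63% | below the first row |

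In the first row the no-effect median on the trial clock is 200 + 0.097/0.00912 - 28 = 183 days.

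Table 8 fixes only the total hazard between days 200 and 352, so all four rows agree with it. The early shape matters in the same way: a hazard that falls over time would also make 200 days too lenient.

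**The case against.** The strongest reply is that the clocks may already agree. Section 12.D.1 says that standard therapy was given when metastatic disease developed, so first metastasis and start of therapy may nearly coincide in the 49 patients. Section 18 describes them as "Among 49 patients who would be considered eligible for this trial and who received standard treatment" and plans accrual from about 40 first metastases a year, which suggests that trial patients might also enter early. Counting from treatment is a sensible and explicit choice. Section 18 also says that the sample size was not formally derived and that the efficacy assessment is preliminary.

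Much of this stands. It supports a small historical gap and rules out calling the misalignment established. It does not state the historical day 0, and it does not bound the gap in trial patients, who need a measurable lesion rather than a recent first metastasis.

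A reader might infer that the comparison is biased, or that the trial has lost a known amount of power. The documents do not support that. The 28-day case also needs a particular hazard shape after day 200, and it does not cover patients who already have several metastases at entry. The 4-week and 6-week windows limit scans and lesion measurement, not time since first metastasis.

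**Conclusion.** The point holds as a question of comparability. Section 18 as written gives the benchmark one origin and the trial another, and the readable text neither reconciles them nor re-estimates the 200 days. Misalignment is possible, not proven; Figure 146, which we cannot see, may label the historical origin.

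If the 200 days does run from first metastasis and trial patients start later, 200 days may not be the no-effect median, and Table 8's power and error rates may not apply. Size and direction are unknown. For an assumed 28-day gap with the early hazard flat, power at ratio 3 under the at-most-2 rule ranges from 36% to 74%, against 66% with no gap, depending on the hazard just after day 200. The direction of the error changes within that range. It should be settled before analysis because the go-forward decision rests on this comparison and the investigators hold the historical records.

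**What to change.** - State in Section 18 the day from which the 49 historical patients were counted.
- Re-estimate their median and the piecewise-exponential curve from start of standard therapy. Use that median in the per-group rule and rerun Table 8 on it. If the 200 days was already counted from that day, a sentence saying so settles the benchmark.
- Use one endpoint definition in Sections 12.D.1 and 18: time from first treatment to new metastasis.
- Record each trial patient's date of first metastasis and report the time from it to Time 0 by group.

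The decision rule keeps its form. The cost is revised wording, one re-run on records already held, and one date per trial patient, with no added patients or visits. The downside is that the stated power may become slightly less favourable.

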The decision to proceed to radiation of the lesions or administer intralesional IFN β -1B will be based on clinical judgment with the following guidelines: 1. If more than one tumor lesions are present at different locations and no critical organ is involved, if feasible, approximately 50% of the lesions should receive radiation or intralesional IFN β -1B initially; 2. At a given time, one patient should receive either radiation or intralesional IFN β -1B but not both modalities; 3. Intralesional IFN β -1B is the preferred modality for patients who have easily palpable superficial lesions (cutaneous, subcutaneous, or lymph nodal metastasis) that can be accurately localized, stabilized by palpation, and are superficial enough to enable intratumoral injections, or patients who have lesions that are attainable through endoscopy; 4. Radiation to a specific lesion or to multiple lesions within a specific field will be administered in the case that multiple radiographically detectable lesions are identified on the pre-treatment scans, lesions are inaccessible by interventional radiology, or the patient refuses intralesional injections. 5. If multiple lesions are present within a tight field, it is recommended not to irradiate some and not others, but rather deliver radiation to the whole field.

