Clinical response assessment of each individual lesions: Response assessment will be done through clinical (for example bi-directional measurements of palpable lesions) or radiographic (for example CT, PET, or MRI) measurement of each lesion at 8 weeks after the first intervention to induce MHC class I upregulation, 8 weeks after the second MHC class I upregulation, if the patient undergoes a second set of T cell infusions, and then at least once every 3 months (12 weeks) or as clinically indicated. Consistency of imaging modality over time is recommended for a given patient. Objective responses in lesions which received MHC Class I upregulation and lesions which did not receive MHC Class I upregulation, will be reported separately. For each individual lesion or group of lesions, a complete response (CR) will be defined as total regression of the lesions, a PR as 30% or greater decrease in the sum of the longest diameter of the lesions compared to baseline and PD as 20% increase in the sum of the longest diameter of the lesions compared to the smallest prior diameter (RECIST v1.1 criteria).

Overall Response Assessment:

A complete response (CR) will be defined as total regression of all tumors, a PR as 30% or greater decrease in the sum of the longest diameter of target lesions compared to baseline and PD as 20% increase in the sum of the longest diameter of target lesions compared to the smallest prior diameter (RECIST v1.1 criteria). This assessment will be performed 8 weeks after the first MHC class I upregulation, 8 weeks after the second MHC class I upregulation, if the patient undergoes a second set of T cell infusions, and then at least once every 3 months (12 weeks) or as clinically indicated.

12.E. Evaluation of Persistence and Function of Adoptively Transferred T Cells

12.E.1. Blood samples

Patients will have 50-60 ml of heparinized blood (green top) and 6 ml of serum (red top) tube drawn during the pre-treatment visit, prior to Avelumab infusion, prior to receiving radiation or intralesional IFN β -1B injections (pre-treatment baseline), prior to tissue biopsy or aspiration, prior to infusion, and at selected time points following infusion (**Appendix B**, research labs). Samples will be used to evaluate the duration of *in vivo* persistence and function of infused T cells, as well as evaluation of MCPyV TAg titers.

All blood samples will be kept at room temperature and sent to room E1-305, FHCRC Research Cell Bank.

12.E.2. Tumor samples

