APPENDIX B

Group 1 Monitoring Schedule^a

GROUP 1		Event	History and PE	Chemistry Panel	CBC	T3 FT4 TSH	Tumor Biopsy	Blood for Research	Radiographic Evaluation	Oncoprotein Serology
Pre-treatment		Evaluation for treatment	X	X	X	X ^f	X ^g	X	X ^b	X
	Day 0	PD-L1 infusion ^c	X	X	X			X		
Week +1/+2	Day +7 - +10	Administer Radiation OR Intralesional IFNβ-1B	X	X	X			X		
Week +2	Day +14	PD-L1 infusion	X	X	X			X		
Week +4	Day +28	PD-L1 infusion	X	X	X		X ^g	X		
Week +6	Day +42	PD-L1 infusion	X	X	X			X		
Week +8	Day +56	PD-L1 infusion	X	X	X			X		
Week +9	Day +63	Staging							X (Day 56-70)	X
Week +10	Day +70	PD-L1 infusion	X	X	X	X ^f		X		
Week +11/+12	Day +77- +80	Administer Radiation OR Intralesional IFNβ-1B (if indicated) ^d	(X)	(X)	(X)			(X)		
Week +12	Day +84	PD-L1 infusion	X	X	X			X		
Week +14	Day +98	PD-L1 infusion	X	X	X			X		
Week +16	Day +112	PD-L1 infusion	X	X	X			X		
Week +18	Day 126	PD-L1 infusion	X	X	X			X		
Week +19	Day +133	Staging							X (Day 126-140)	X
Week +20	Day +140	PD-L1 infusion	X	X	X			X		
Week +22	Day +154	PD-L1 infusion	X	X	X	X ^f		X		
Week +24	Day +168	PD-L1 infusion	X	X	X			X		
Beyond +52 weeks		Study ends	X ^e	X ^e	X ^e			X ^e	X ^e	X
Beyond +24 weeks infusion Q2 weeks for up to 1 year total on treatment		PD-L1 infusion	X	X	X			X		

Test results and procedures conducted as per standard of care may be used for eligibility determination and evaluation for toxicity.

^a The dates listed on the study calendar above are approximate as many patients are expected to reside out of state and his oncologists and laboratories may not always be able to follow the time points as dictated by the protocol.

^b Includes brain evaluation.

^c Patients may receive preferably one, but up to 3 infusions of anti-PD-L1 before the first MHC class I up-regulation intervention.

^d The MHC class I upregulation can be repeated once, at any time point, if there is radiological disease present.

Treatment must start within 4 weeks of the preceding radiological evaluation.

^e At least every 3 months for one year, every 6 months for one year then yearly and as clinically indicated.

^f at baseline, at cycle 6 and then every 6 cycles.

^gIf accessible.

Group 2 Monitoring Schedule^a

GROUP 2		Event	History and PE	Chemistry	CBC	T3 FT4 TSH	Tumor Biopsy	Blood for Research	Radiographic Evaluation	Oncoprotein Serology
Pre-treatment	Evaluation for treatment	X	X	X	X	X ^f	X ^g	X	X ^b	X
	Day 0	PD-L1 infusion ^c	X	X	X			X		

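### Lesion response is split by receipt of MHC up-regulation with no date for setting that status, so later local treatment of persisting lesions can inflate the untreated-lesion response rate

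*Combined protocol and SAP*

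**What the plan says.** Section 18 states that overall RECIST response may not capture the effect of the T cells or the anti-PD-L1 antibody, because radiation or interferon can act directly on the lesion it targets. For patients with both kinds of lesion it therefore reports response separately in "all lesions which received MHC Class I upregulation and all lesions which did not receive MHC Class I upregulation". It calls for "The Objective response rate (ORR) and 90% confidence interval" to be "calculated as the proportion of evaluable lesions that achieve a CR or PR", separately for the two sets, with intervals that allow for correlation within a patient. It gives no date for fixing a lesion's status and no scan at which response is read.

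Section 10.E says that the choice between radiation and injection "will be based on clinical judgment with the following guidelines". The first guideline is that, where feasible, "approximately 50% of the lesions should receive radiation or intralesional IFN" beta-1B, and it describes this as the initial treatment.

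For Group 1, footnote d of Appendix B says: "The MHC class I upregulation can be repeated once, at any time point, if there is radiological disease present". The Group 2 footnote sets the same condition for repeating up-regulation together with the T-cell infusions. Section 6 also ties the repeat to continued detectable disease.

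Section 12.D.2 assesses each lesion 8 weeks after the first intervention, "8 weeks after the second MHC class I upregulation, if the patient undergoes a second set of T cell infusions", and then at least every 3 months. Partial response is always judged against baseline. Appendix B schedules staging at day 63 (window 56-70), the optional repeat at day 77-80, and staging again at day 133 (window 126-140), in both groups.

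**The concern.** A lesion left alone at day 7-10, still present at day 63 and irradiated at day 77-80 has, by day 133, received up-regulation. The plan does not say which set it then belongs to. A lesion that has disappeared cannot be treated at the repeat, so which lesions change status depends on how they have responded.

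If such a lesion moves to the treated set, the untreated set loses mainly lesions that had not responded. If it stays in the untreated set and its later scans count, shrinkage caused by local treatment is read as a systemic effect. The split is there to separate local from systemic effect, so either outcome defeats its purpose. Allowing for within-patient correlation changes the width of the interval, not the bias of the estimate.

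**Working it through.** The plan gives no expected value, power or precision for the lesion-level response rate, so there is no figure of its own to reproduce.

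**Inputs from the documents:** undated status (Section 18); about half of lesions treated at first (10.E); repeat conditional on visible disease and not restricted to lesions already treated (Section 6, Appendix B); assessment against baseline continuing after the repeat (12.D.2).

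**Inputs assumed, because the documents do not give them:**
- p: true response rate of initially untreated lesions
- f: share of non-responding untreated lesions treated later
- g: share of responding untreated lesions treated later (for example a partial response with visible remnant)
- r: share of late-treated non-responders that then meet the response criterion

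**Reading A: status means treated at any time.** Responders left in the untreated set are p(1-g); non-responders left are (1-p)(1-f). The reported rate is

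p(1-g) / [p(1-g) + (1-p)(1-f)]

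This exceeds p exactly when f > g. For p = 25% and f = 50%:
- g = 0: 0.25 / (0.25 + 0.375) = 40%
- g = 25%: 0.1875 / (0.1875 + 0.375) = 33%
- g = 50%: 0.125 / (0.125 + 0.375) = 25%, no bias

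With g = 0 and p = 25%, f = 25% gives 0.25 / (0.25 + 0.5625) = 31% and f = 75% gives 0.25 / (0.25 + 0.1875) = 57%. With g = 0 and f = 50%, p = 10%, 20%, 30%, 40% and 50% become 18%, 33%, 46%, 57% and 67%.

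A simulation with 10 patients, two untreated lesions each and within-patient correlation 0.3 (all assumed) gave 33% to 34% for p = 20%, f about 50% and g = 0. The formula gives 0.20 / (0.20 + 0.40) = 33%, so clustering leaves the bias in place.

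**Reading B: status fixed at the first intervention, later scans counted.** The reported rate is p + (1-p) x f x r. For p = 25% and f = 50%:
- r = 25%: 0.25 + 0.75 x 0.5 x 0.25 = 34%
- r = 50%: 0.25 + 0.75 x 0.5 x 0.5 = 44%
- r = 75%: 0.25 + 0.75 x 0.5 x 0.75 = 53%

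**Reading C: response read only at the scan 8 weeks after the first intervention.** Day 7-10 plus 56 days is day 63-66, inside the day 56-70 window and before the scheduled repeat at day 77-80. No lesion has changed status, and the estimate is p as it stands at that scan.

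**The case against.** The strongest reply is that the plan states no treated-at-any-time rule. A reader might infer that non-responders are bound to leave the untreated set, or that every reading biases the rate upward. The documents support neither: the wording is undated, and 12.D.2 lists the 8-week assessment separately, so Reading C is open and unbiased. Reading B also sits awkwardly with the words of Section 18, since it keeps an irradiated lesion among those that did not receive treatment. This stands, but the plan does not choose Reading C, and its assessments continue after the repeat.

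Second, the repeat is triggered by visible disease in the patient, not by non-response of a given lesion, so a partially responding lesion can be treated too. This also stands, which is why g is in the formula. Section 10.C does name tumor reduction without clearance as an example where up-regulation may not be indicated before the second set of infusions. That makes g < f plausible, but it is an example and does not make g zero.

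Third, f may be small. The repeat is optional, Section 10.C permits re-irradiation of treated sites, and under Section 13.G patients whose progression urgently needs other drugs leave the protocol. Nothing in the documents supports a particular f, and f = 75% is only the upper end of an assumed range.

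Fourth, a reader might take this split for the plan's main test of systemic effect. Sections 3.J, 12.D.1 and 18 give that role to time to new metastasis, and the choice of treatment to take forward rests on it. The lesion split carries no hypothesis or threshold.

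**Conclusion.** The gap is real and limited. As written, the analysis lets a lesion's class, or its counted response, depend on treatment that is given only when disease persists. Under Reading A the bias is upward if f > g; under Reading B it is upward if any late-treated non-responder then shrinks enough to count. It is zero if no initially untreated lesion is treated later, or if response is read only at the day 56-70 scan.

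The size cannot be computed from the documents. For p = 25% and f = 50%, both assumed, Reading A gives 25% to 40% as g runs from 50% to 0. It would go too far to say that the plan will overstate systemic activity in both groups: p, f, g and r are unknown and the repeat is optional. The endpoint is secondary and descriptive, in at most 10 patients per group and only those with both kinds of lesion. The primary endpoint and the selection between groups are untouched. The wording should be corrected before the lesion data are analyzed.

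**What to change.** Add to Section 18:

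1. Set each baseline lesion's class at the first MHC intervention, and use that class to decide which patients have both kinds of lesion.
2. Report response in treated and untreated lesions at the common scan 8 weeks after that intervention (day 56-70 on the Appendix B schedule). Tie the landmark to the intervention, because Section 6 lets it follow up to three avelumab infusions.
3. Also report best response. For initially untreated lesions use only scans before that lesion's own local treatment, and keep those lesions in the untreated denominator with the status reached by then.
4. Report lesions first treated at the second intervention as a separate category, with the scan before that treatment as their baseline.

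No treatment or visit changes. The costs are a possibly lower untreated-lesion rate, and delayed systemic responses that go uncounted in late-treated lesions while never-treated lesions keep full follow-up. The common scan in item 2 is there because it treats all lesions alike. Treatment dates must be captured lesion by lesion; the documents do not say that they are.
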